### 8.3. Death

If one or more patients die during the study, a listing of deaths will be provided (Listing 16.2.7.4).

### 8.4. Clinical Laboratory Tests

Laboratory values and changes from baseline (Visit 4 or the last available value pre-dosing study medication) to endpoint (Visit 7) in laboratory test results (in standard international (SI) units)) will be presented, by treatment group and overall, using descriptive summary statistics (n, mean, SD, median, min, max), based on the safety analysis set (Part 2), for serum chemistry (Summary 15.3.2.1), and for serum hematology values and changes from baseline to each post-baseline visit (Summary 15.3.2.2). Urinalysis tests performed at Visits 4 and 7 will be summarized in Summary 15.3.2.3. Specific clinical laboratory tests performed at Screening (Visit 1) and at various visits throughout the study are presented in Table 2 below.

**Table 2. Clinical Laboratory Tests**

Serum Chemistry	Hematology	Urinalysis
β human chorionic gonadotropin (HCG) a	hemoglobin	B-HCG a
calcium	hematocrit	protein
phosphate	red blood cell (RBC) count	glucose
sodium	RBC indices	ketones
potassium	platelet count	blood (hemoglobin)
chloride	white blood cell (WBC) count, and differential count and percentage	pH
creatinine	– absolute neutrophil count (ANC)	specific gravity
glucose	– polymorphonuclear leukocytes (neutrophils)	microscopic
blood urea nitrogen (BUN)	– lymphocytes	– bacteria
cholesterol (low density lipoprotein [LDL]/high density lipoprotein [HDL]/total) a	– eosinophils	– red blood cells (RBCs)
triglycerides a	– monocytes	– white blood cells (WBCs)
uric acid	– basophils	
alanine aminotransferase (ALT)	– atypical lymphocytes	
aspartate aminotransferase (AST)	– other (to include band granulocytes)	
lactate dehydrogenase (LDH)	international normalized ratio (INR)	
gamma-glutamyl transpeptidase (GGT)		
alkaline phosphatase		
bicarbonate or carbon dioxide		
creatinine phosphokinase		
total protein		
albumin		
total bilirubin		
direct bilirubin		
indirect bilirubin		

a Assessed at the screening visit only.

Shifts (below, within, and above the normal range) from baseline (Visit 4) to each post-baseline visit (hematology) and to endpoint (Visit 7, serum chemistry and urinalysis) will be summarized, by treatment group and overall based on the safety analysis set (Part 2), using patient counts (n) for each serum chemistry lab test (Summary 15.3.2.4), for each hematology lab test (Summary 15.3.2.5), and for each urinalysis lab test (Summary 15.3.2.6).

The incidence of post-baseline (including scheduled, unscheduled, and withdrawal visits) potentially clinically significant abnormal (PCS) abnormal values will be summarized for serum chemistry, hematology and urinalysis laboratory tests (Summaries 15.3.2.7, 15.3.2.8, and 15.3.2.9, respectively), using descriptive statistics (n, %) with the criteria for potentially clinically significant specified in Table 3 below.

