## **8. SAFETY ANALYSIS**

### **8.1. General**

The safety analyses for Part 2 of the study will be presented by treatment group and overall, based on the safety analysis set.

In addition, safety analysis for Part 1, based on the enrolled analysis set, will be presented by study participants status (HCs vs patients with asthma) and overall.

Combined safety analysis presenting safety data for Part 1 and Part 2 of the study may be provided, as deemed necessary.

Individual listings will also be provided.

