### **8.2. Adverse Events**

All adverse events will be coded using the latest available version of the Medical Dictionary for Regulatory Activities (MedDRA), associated with five levels of classifications: a System Organ Class (SOC), a High Level Group Term (HLGT), a High Level Term (HLT), a Preferred Term (PT) and a lowest Level Term (LLT).

Only Treatment Emergent Adverse Event (TEAE), defined as events occurring after the first drug administration and until the end of the study, will be presented, based on Safety analysis set.

Similarly, AEs occurring between ICF signing and end of Part 1 will be presented based on Enrolled analysis set.

In the AE summary tables each patient will be counted only once in each preferred term or system organ class category for the analyses of safety. Summaries will be presented for all adverse events by treatment group, and overall as following:

- All AEs sorted by SOC and PT based on Safety analysis set (Summary 15.3.1.1) and on Enrolled analysis set (Summary 15.3.1.2)
- All AEs sorted by PT based on Safety analysis set (Summary 15.3.1.3) and on Enrolled analysis set (Summary 15.3.1.4)
- Treatment-related AE sorted by SOC and PT based on Safety analysis set (Summary 15.3.1.5)
- Serious AE sorted by SOC and PT based on Safety analysis set (Summary 15.3.1.6)
- Non serious AE sorted by SOC and PT based on Safety analysis set (Summary 15.3.1.7)
- AE sorted by SOC, PT and severity based on Safety analysis set (Summary 15.3.1.8).

Asthma deterioration will be descriptively summarized for safety analysis set (Summary 15.3.1.9).

Patient listings of serious adverse events and adverse events leading to withdrawal will be presented. Suspected anaphylaxis/hypersensitivity and CPK reactions will be listed individually (Listings 16.2.8.12 and 16.2.8.13).

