**Table 3. Criteria for Potentially Clinically Significant Laboratory Values**

Test	Criterion value*
Alanine aminotransferase (ALT)	≥ 3x ULN
Aspartate aminotransferase (AST)	≥ 3x ULN
Alkaline phosphatase	≥ 3x ULN
Gamma-glutamyl transpeptidase (GGT)	≥ 3x ULN
Lactate dehydrogenase (LDH)	≥ 3x ULN
Blood urea nitrogen (BUN)	≥ 10.71 mmol/L
Creatinine	≥ 177 mmol/L
Uric acid Men	≥ 625 mmol/L
Uric acid Women	≥ 506 mmol/L
Bilirubin (total)	≥ 34.2 mmol/L
Hematology	
Hematocrit Men	< 0.37 L/L
Hematocrit Women	< 0.32 L/L
Hemoglobin Men	≤ 115 g/L
Hemoglobin Women	≤ 95 g/L
Hemoglobin Adolescents (12 to 17 years)	≤ 100 g/L
White blood cell (WBC) counts	≤ 3 x 10  /L
	≥ 20 x 10  /L
Eosinophils	≥ 10%
Absolute neutrophil counts (ANC)	≤ 1 x 10  /L
Platelet counts	≤ 75 x 10  /L
	≥ 700 x 10  /L
Urinalysis	
Blood (HGB)	≥2 unit increase from baseline
Glucose	≥ 2 unit increase from baseline
Ketones	≥ 2 unit increase from baseline
Total protein	≥ 2 unit increase from baseline

\* ULN=upper limit of normal range.

For Creatine phosphokinase (CPK) parameter, no PSC will be calculated but the grading scale of the Guidance for Industry Toxicity Grading Scale for Healthy Adult and Adolescent Volunteers Enrolled in Preventive Vaccine Clinical Trials will be used to classify subjects in the four following grades (Summary 15.3.2.9) :

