## 8.6. Vital Signs

Vital signs (blood pressure, respiratory rate, body temperature, pulse, and blood oxygen saturation (SpO2)) will be measured at Screening (Visit 1) and at Visits 4, 5, 6 and 7. All vital signs results outside of the reference ranges will be judged by the investigator as belonging to one of the following categories:

- abnormal and not clinically significant
- abnormal and clinically significant

Any abnormal vital sign value that is judged by the investigator as clinically significant will be recorded on the source documentation, transcribed to the CRF as an adverse event.

Summary statistics for vital signs: blood pressure, respiratory rate, body temperature, pulse, and SpO2 will be presented at baseline (visit 4), visit 5, visit 6 and visit 7 and will include:

- Vital signs values and changes from baseline (Visit 4) to each post-baseline visit will be summarized, by treatment group, based on the safety analysis set, using descriptive statistics (Summary 15.3.3.1). Individual listings will also be provided.
- Summaries of potentially clinically significant (PCS) abnormal values will include all post-baseline values (including scheduled, unscheduled, and withdrawal visits). The incidence of potentially clinically significant abnormal values will be summarized (Summary 15.3.3.2) using descriptive statistics (n, %) with the criteria for potential clinical significance abnormal values specified in Table 5 below.

Note that in order to qualify as potentially clinically significant abnormal, a value needs to meet both criteria below: i.e., have a value beyond the criterion value and a change of at least the magnitude specified in the change relative to baseline column.

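### Laboratory PCS counts in SAP 8.4 take no account of the pre-dose value, and the eosinophils ≥10% row partly restates the entry condition, so its flags will fall mainly on placebo

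*SAP*

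**What the plan says.** **PCS rule.** SAP 8.4 reads: "The incidence of post-baseline (including scheduled, unscheduled, and withdrawal visits) potentially clinically significant abnormal (PCS) abnormal values will be summarized for serum chemistry, hematology". Urinalysis has its own count too (Summaries 15.3.2.7 to 15.3.2.9 in all), and the limits are in SAP Table 3. The chemistry rows are multiples of ULN or fixed concentrations. The haematology rows are fixed values, one of which is eosinophils at 10% or more. None of these rows mentions the patient's own V4 value.

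**Contrast within the same SAP.** Each urinalysis row of Table 3 requires at least a "2 unit increase from baseline". For vital signs, SAP 8.6 asks a reading to "have a value beyond the criterion value and a change of at least the magnitude specified in the change relative to baseline column". Only a few rows of Table 5 (low respiratory rate, low temperature, SpO₂) state no change.

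**CPK.** No PCS count is planned. A published toxicity scale, given in SAP Table 4, "will be used to classify subjects in the four following grades (Summary 15.3.2.9"). The text names no visit, no rule for choosing among several values and no V4 grade.

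**Other planned laboratory outputs.** SAP 8.4 also summarises "Laboratory values and changes from baseline (Visit 4 or the last available value pre-dosing study medication) to endpoint (Visit 7") for chemistry, and "Shifts (below, within, and above the normal range) from baseline (Visit 4) to each post-baseline visit (hematology") or to V7 (chemistry, urinalysis). SAP 8.1 adds "Individual listings will also be provided", and SAP 8.2 adds "Suspected anaphylaxis/hypersensitivity and CPK reactions will be listed individually".

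**The concern.** A table of post-baseline PCS values is normally read as showing what appeared after dosing. With absolute limits and no V4 reference, a patient who was beyond the limit before the infusion and stays there is counted exactly like one who crossed it afterwards.

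For the eosinophil row the problem is also the row itself. It reports the trait that patients were selected for as a laboratory safety abnormality, in a trial of a drug whose expected effect is to lower it (Protocol 1.3.2.2, Laboratory Findings). Read alone, the haematology PCS table could show a difference between arms that is untreated disease on placebo and intended pharmacology on reslizumab.

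CPK elevation is a named adverse reaction (Protocol 1.4.1.2), so a grade table that cannot show worsening from a raised pre-dose value gives less than it could. At stake is how readable the descriptive safety tables are, not any efficacy result.

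**Working it through.** The plan gives no figure of its own here. The check is a comparison of rules plus simple arithmetic.

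**1. Can a value beyond a Table 3 limit be present at V4?** Protocol 4.2 excludes glucose of 150 mg/dL or more (c) and compromised renal function (s). It also excludes clinically meaningful comorbidity (f), which is a matter of judgement. Neither 4.1 nor 4.2 sets a numeric limit for liver enzymes, haemoglobin, white cells or platelets. Such values are therefore possible at V4. The documents give no rate for them, and limits such as 3 × ULN or platelets ≤75 × 10⁹/L suggest they would be uncommon.

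**2. Eosinophil row against the entry condition.** Inputs: entry at 400/µL or more (Protocol 4.1, h); PCS at 10% or more (SAP Table 3). White counts are not in the documents, so the range below is an assumption.

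- Percentage at the entry limit = 100 × 400 / white count per µL
- Absolute count needed for the PCS flag = 0.10 × white count per µL

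| White count (×10⁹/L) | 400/µL as % | Count needed for 10% (/µL) |
|---|---|---|
| 4.0 | 10.0 | 400 |
| 6.0 | 6.7 | 600 |
| 7.0 | 5.7 | 700 |
| 8.0 | 5.0 | 800 |
| 10.0 | 4.0 | 1000 |

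At a white count of 4.0 or less, anyone still at the entry level is flagged. Above that, only patients with higher counts are. Some patients, not all, will meet the row before dosing. After dosing, those on reslizumab should mostly drop below it and those on placebo should not.

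**3. Would a V4 split alone repair this row?** No. A placebo patient whose eosinophils vary around 10% can be below the limit at V4 and above it at week 2, 4 or 6. A split would call that newly occurring, although it is still the disease under study.

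**4. CPK: what each planned output shows for a patient at Grade 1 at V4 and Grade 2 at V7.**

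- Grade table (Summary 15.3.2.9): no V4 grade, so no sign of the worsening.
- Normal-range shift table (Summary 15.3.2.4; CPK is in the chemistry column of SAP Table 2): above normal to above normal. Pre-existing elevation is visible, the change of grade is not.
- Adverse events: Protocol 7.1.7.2 requires a CPK of 3.1 × ULN or more to be recorded as an adverse event. Grade 2 ends at 3.0 × ULN, so that threshold is not reached.
- Individual listings: visible.

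A patient normal at V4 and raised at V7 is already separated from one raised at both visits by the shift table. The gap is worsening from one raised value to another below 3.1 × ULN.

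**5. How often might pre-dose CPK be raised?** Earlier studies had elevated baseline CPK in 14% and 9% of the two arms (Protocol 1.3.2.2). These are pre-dose rates, so a common rate is applied to all patients here:

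- At least one of 10: 1 − 0.91¹⁰ = 0.61; 1 − 0.86¹⁰ = 0.78
- At least one in an arm of 5: 1 − 0.91⁵ = 0.38; 1 − 0.86⁵ = 0.53

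If elevated means above ULN (an assumption), these are upper limits, at those rates, for Grade 1 or higher, because Grade 1 starts at 1.25 × ULN.

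**The case against.** The best defence is that absolute limits alongside change and shift tables are a legitimate layout, and that with 10 patients the listings show everything. Splitting arms of 5 by V4 status gives many cells of 0 or 1. Eosinophil counts and changes are reported by arm and visit under SAP 6.3.1, so the PCS row misleads only someone who reads it alone. An investigator could exclude a patient with grossly abnormal laboratory results under exclusion (f).

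Most of this stands and sets the size of the point. It does not rescue the eosinophil row, which adds nothing to 6.3.1 and presents it as a safety signal. Nor does it explain why chemistry and haematology lack the baseline reference that urinalysis and most vital signs have.

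A reader might infer that the plan cannot separate new from pre-existing CPK elevation. The documents do not support that: the V4-to-V7 shift table does so by arm, and the adverse-event rule covers 3.1 × ULN and above.

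A reader might also see the missing worst-value rule as a serious gap. Protocol 3.14.3.2 schedules post-dose chemistry only at week 6 (V7), and SAP 8.4 summarises it there, so there is normally one post-dose value. SAP 4.4 gives a last-value rule for by-visit summaries. SAP Table 1 appears to mark chemistry at further visits, but 8.4 does not summarise it at those visits.

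The double use of Summary 15.3.2.9 (urinalysis PCS and CPK grades) and the ungraded values between 1.5 and 1.6 and between 3.0 and 3.1 × ULN in Table 4 are clerical.

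**Conclusion.** The point holds as a minor one. Chemistry and haematology PCS counts include abnormalities present before dosing. The eosinophils ≥10% row partly overlaps the entry condition and will mainly flag placebo patients for reasons unrelated to safety. The CPK grade table does not show worsening from a pre-dose elevation, but other planned outputs leave only a small gap.

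The conclusion on eosinophils rests on the expected drug effect stated in the protocol; the overlap figures rest on assumed white counts. It is tempting to state an expected number of flagged placebo patients. The documents do not support one, because they give neither white counts nor an eosinophil distribution. Simulation with every input assumed gave 20% to 84% of untreated patients flagged at one or more post-dose visits, and about 15% to 80% when eosinophils were allowed to contribute to the white count. That says little beyond some but not all.

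It is equally tempting to carry the 14% against 9% pre-dose CPK difference into these arms. Nothing suggests it would recur here.

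One patient is 1/5, or 20 percentage points, of an arm, so a single misread flag looks large. No endpoint or trial decision changes.

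**What to change.** In SAP 8.4, before unblinding:

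- Remove the eosinophils ≥10% row from Table 3, or label it pharmacodynamic and refer to 6.3.1.
- In Summaries 15.3.2.7 and 15.3.2.8, keep every post-dose count but split it by whether the same criterion was met at V4 (or the last pre-dose value, as 8.4 already allows).
- Tabulate CPK as V4 grade by worst post-dose grade, keeping the named scale. Give the table its own Summary number and state a rounding rule in the same edit.

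The cost is SAP wording and minor reprogramming of three descriptive tables. No new data are needed: Protocol 3.14.3.1 and 3.14.3.2 already schedule haematology at V4 and weeks 2, 4 and 6, and chemistry at V4 and week 6. The only downside is slightly wider tables with small cells.

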**Table 3. Criteria for Potentially Clinically Significant Laboratory Values**

Test	Criterion value*
Alanine aminotransferase (ALT)	≥ 3x ULN
Aspartate aminotransferase (AST)	≥ 3x ULN
Alkaline phosphatase	≥ 3x ULN
Gamma-glutamyl transpeptidase (GGT)	≥ 3x ULN
Lactate dehydrogenase (LDH)	≥ 3x ULN
Blood urea nitrogen (BUN)	≥ 10.71 mmol/L
Creatinine	≥ 177 mmol/L
Uric acid Men	≥ 625 mmol/L
Uric acid Women	≥ 506 mmol/L
Bilirubin (total)	≥ 34.2 mmol/L
Hematology	
Hematocrit Men	< 0.37 L/L
Hematocrit Women	< 0.32 L/L
Hemoglobin Men	≤ 115 g/L
Hemoglobin Women	≤ 95 g/L
Hemoglobin Adolescents (12 to 17 years)	≤ 100 g/L
White blood cell (WBC) counts	≤ 3 x 10  /L
	≥ 20 x 10  /L
Eosinophils	≥ 10%
Absolute neutrophil counts (ANC)	≤ 1 x 10  /L
Platelet counts	≤ 75 x 10  /L
	≥ 700 x 10  /L
Urinalysis	
Blood (HGB)	≥2 unit increase from baseline
Glucose	≥ 2 unit increase from baseline
Ketones	≥ 2 unit increase from baseline
Total protein	≥ 2 unit increase from baseline

\* ULN=upper limit of normal range.

For Creatine phosphokinase (CPK) parameter, no PSC will be calculated but the grading scale of the Guidance for Industry Toxicity Grading Scale for Healthy Adult and Adolescent Volunteers Enrolled in Preventive Vaccine Clinical Trials will be used to classify subjects in the four following grades (Summary 15.3.2.9) :

**Table 4. Toxicity Grading Scale for Healthy Adult and Adolescent Volunteers**

	Mild (Grade 1)	Moderate (Grade 2)	Severe (Grade 3)	Potentially Life Threatening (Grade 4)
CPK	1.25 – 1.5 x ULN	1.6 – 3.0 x ULN	3.1 – 10x ULN	> 10 x ULN

#### 8.4.1. Other Clinical Laboratory Tests

Human chorionic gonadotropin tests ( $\beta$ -HCG) in serum will be performed at screening (Visit 1) only for all participating women of child bearing potential. Urine  $\beta$ -HCG tests will be performed for all participating women of child bearing potential at V2, V3, V4, V5, V6, and V7, before study drug administration and before each PET/CT scan.

Capillary blood glucose will be performed before each PET/CT scan (V2, V3, V5, V6 and V7) to check the glucose level. If a threshold is raised (determined by the investigator), the scan is canceled or postponed. Test results (in standard international (SI) units)) will be presented, by treatment group and overall, using descriptive summary statistics (n, mean, SD, median, min, max), based on the enrolled analysis set (Part 1) and safety analysis set (Part 2).

#### 8.5. Physical Examinations

Complete physical examinations, including height and weight (to be obtained at screening visit only) are to be performed at Visit 1 and Visit 7.

The “full” physical examination should include the following organ systems: General appearance; Head, Eyes, Ears, Nose, and Throat; Chest and Lung; Heart; Abdomen; Musculoskeletal; Skin; Lymph Nodes; and Neurological.

The “brief” physical examination recorded at Visits 4, 5, and 6 (Part 2) only should include at minimum the following organ systems: General appearance; Head, Eyes, Ears, Nose, and Throat; Chest and Lung; and Heart.

Any physical examination finding that is judged by the investigator as clinically significant will be considered as an adverse event, recorded on the CRF in the same way and will then be displayed with AEs (Summaries 15.3.1).

Newly occurring abnormalities in the physical examinations will be identified and listed.

Only percentages of subjects with physical abnormalities will be displayed in the safety part (Summary 15.3.4.1).

## 8.6. Vital Signs

Vital signs (blood pressure, respiratory rate, body temperature, pulse, and blood oxygen saturation (SpO2)) will be measured at Screening (Visit 1) and at Visits 4, 5, 6 and 7. All vital signs results outside of the reference ranges will be judged by the investigator as belonging to one of the following categories:

- abnormal and not clinically significant
- abnormal and clinically significant

Any abnormal vital sign value that is judged by the investigator as clinically significant will be recorded on the source documentation, transcribed to the CRF as an adverse event.

Summary statistics for vital signs: blood pressure, respiratory rate, body temperature, pulse, and SpO2 will be presented at baseline (visit 4), visit 5, visit 6 and visit 7 and will include:

- Vital signs values and changes from baseline (Visit 4) to each post-baseline visit will be summarized, by treatment group, based on the safety analysis set, using descriptive statistics (Summary 15.3.3.1). Individual listings will also be provided.
- Summaries of potentially clinically significant (PCS) abnormal values will include all post-baseline values (including scheduled, unscheduled, and withdrawal visits). The incidence of potentially clinically significant abnormal values will be summarized (Summary 15.3.3.2) using descriptive statistics (n, %) with the criteria for potential clinical significance abnormal values specified in Table 5 below.

Note that in order to qualify as potentially clinically significant abnormal, a value needs to meet both criteria below: i.e., have a value beyond the criterion value and a change of at least the magnitude specified in the change relative to baseline column.

**Table 5. Criteria for Potentially Clinically Significant Vital Signs**

Vital Sign	Criterion value	Change relative to baseline
Pulse	>100 bpm	Increase of ≥30
	<50 bpm	Decrease of ≥30
Systolic blood pressure	>160 mm Hg	Increase of ≥30
	<90 mm Hg	Decrease of ≥30
Diastolic blood pressure	>100 mm Hg	Increase of ≥12
	<50 mm Hg	Decrease of ≥12
Respiratory rate	>24 breaths/min	Increase of ≥10
	<6 breaths/min	Not applicable
Temperature	<96.5°Fahrenheit	Not applicable
	>100.5°Fahrenheit	Increase of ≥2
SpO 2	pulse oximeter <88%	

## 8.7. Electrocardiography

Any abnormal ECG value that is judged by the investigator at the screening visit (or at unscheduled visit if applicable) as clinically significant will be recorded as an adverse event.

The incidence of patients meeting PCS thresholds for each QTc Bazett and Fridericia interval will be summarized (Summary 15.3.X.X) using descriptive statistics (n, %).

The predefined threshold values for absolute QTc Bazett and Fridericia interval prolongations at baseline are > 450 msec and > 500 msec.

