3.14.1. Procedures for Screening and Enrollment (Visit 1)

A signed and dated informed consent form will be obtained before any screening procedures commence (see Section 12.1). Assessments conducted as part of routine medical care and performed during the screening period may be used in place of the protocol-specific assessments. In addition, disease-specific assessments performed within a specified time frame before informed consent may be used for the study. Patients will acknowledge and agree to the possible use of this information for the study by giving informed consent.

After informed consent is obtained, patients who are screened will be assigned an 8-digit permanent identification number such that all patients from each investigational center are given consecutive identification numbers in successive order of inclusion. The first 2 digits of the screening number will be the number assigned to the country where the investigational center is located, the next 3 digits will be the assigned number of the investigational center, and the last 3 digits will be assigned at the investigational center (eg, if the number assigned to the country is 01, the 3rd patient screened at 5th investigational center would be given the number of 01005003).

The screening visit (visit 1) will take place not more than 3 weeks before the Part 1 baseline visit (visit 2). The following procedures will be performed at visit 1:

- Obtain written informed consent before any study-related procedures are performed
- Review inclusion and exclusion criteria
- Review medical history
- Review medication history
- Review smoking history
- Perform clinical laboratory tests (chemistry, hematology, and urinalysis). Patients with an eosinophil count $<400/\mu\text{L}$ may be retested up to 2 additional times within the 21-day screening period. Patients must have an eosinophil level $\geq400/\mu\text{L}$ to complete screening.
- Perform serum pregnancy test (for women of childbearing potential)
- Perform complete physical examination including height and weight
- Assess vital signs, including blood pressure (BP), pulse, respiratory rate (RR), body temperature, and blood oxygen saturation level (SpO₂)
- Perform ECG
- Perform spirometry
- Collect sputum sample
- Complete ACQ-6 (patients only, not HC subjects)
- Inquire about adverse events
- Inquire about concomitant medication usage
- Inform patients of study restrictions and compliance requirements

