7.1. Adverse Events

7.1.1. Definition of an Adverse Event

An adverse event is any untoward medical occurrence in a patient administered a pharmaceutical product, regardless of whether it has a causal relationship with this treatment.

In this study, any adverse event occurring after the clinical study patient has signed the informed consent form should be recorded and reported as an adverse event.

An adverse event can, therefore, be any unfavorable and unintended physical sign, symptom, or laboratory parameter that develops or worsens in severity during the course of this study, or significant worsening of the disease under study, or of any concurrent disease, whether or not considered related to the study drug. A new condition or the worsening of a pre-existing condition will be considered an adverse event. Stable chronic conditions (such as arthritis) that are present before study entry and do not worsen during this study will not be considered adverse events.

Accordingly, an adverse event can include any of the following:

- intercurrent illnesses
- physical injuries
- events possibly related to concomitant medication
- significant worsening (change in nature, severity, or frequency) of the disease under study or other pre-existing conditions (Note: A condition recorded as pre-existing that is intermittently symptomatic [eg, headache] and that occurs during this study should be recorded as an adverse event.)
- drug interactions
- laboratory or diagnostic test abnormalities that result in the withdrawal of the patient from the study, are associated with clinical signs and symptoms or a serious adverse event, require medical treatment or further diagnostic work up, or are considered by the investigator to be clinically significant (Note: Abnormal laboratory test results at

the screening visit that preclude a patient from entering the study or receiving study treatment are not considered adverse events.)

Worsening of the disease under study (ie, asthma) including asthma exacerbations requiring additional controller medication, will be collected as an efficacy assessment in this study. The aforementioned worsening of asthma should be recorded as an adverse event only if the presentation or outcome is more severe than would typically be expected from the normal course of the disease in a particular patient.

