7.5. Vital Signs

Vital signs (blood pressure, respiratory rate, body temperature, pulse, and SpO₂) will be measured at the time points detailed in [Table 2](#). All vital signs results outside of the reference ranges will be judged by the investigator as belonging to one of the following categories:

- abnormal and not clinically significant
- abnormal and clinically significant

Before blood pressure and pulse are measured, the patient must be in a supine or semi-erect/seated position and resting for at least 5 minutes. The same position and arm should be used each time vital signs are measured for a given patient. For any abnormal vital sign finding, the measurement should be repeated as soon as possible. Any vital sign value that is judged by the investigator as clinically significant will be recorded on the source documentation, transcribed to the CRF as an adverse event, and monitored as described in Section [7.1.2](#).

7.6. *Electrocardiography*

A 12-lead ECG will be conducted at screening (visit 1). ECGs should be obtained before other assessments (eg, blood draw and pulmonary function testing). The ECG will be interpreted by the investigator (or qualified physician) as normal or abnormal. If the ECG is read as abnormal the investigator will specify the abnormality and indicate whether or not the abnormality is clinically significant (yes or no). Clinically significant abnormal ECG findings at screening should be recorded as part of the medical history.

7.7. *Physical Examinations*

Physical examinations, including height (to be obtained at the screening visit only) and weight, will be performed at the time points detailed in [Table 2](#). The “full” physical examination should include the following organ systems: General appearance; Head, Eyes, Ears, Nose, and Throat; Chest and Lung; Heart; Abdomen; Musculoskeletal; Skin; Lymph Nodes; and Neurological. The “brief” physical examination should include at minimum the following organ systems: General appearance; Head, Eyes, Ears, Nose, and Throat; Chest and Lung; and Heart. Any physical examination finding that is judged by the investigator as clinically significant will be considered an adverse event, recorded on the CRF, and monitored as described in Section [7.1.2](#).

7.8. *Concomitant Medication or Treatment*

Use of concomitant medication or treatment will be monitored throughout the study. Details of prohibited medications are found in Section [5.3](#).

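### SAP 8.7 makes a clinically significant screening ECG finding an adverse event, while Protocol 7.6 makes it medical history; only the Part 1 adverse event tables can be affected

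*SAP*

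**What the plan says.** **SAP 8.7 (Electrocardiography).** An abnormal ECG value at the screening visit, or at an unscheduled visit if there is one, that the investigator judges "as clinically significant will be recorded as an adverse event".

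**Protocol 7.6 (Electrocardiography).** One ECG is scheduled, at visit 1. The rule for it is: "Clinically significant abnormal ECG findings at screening should be recorded as part of the medical history". The schedules of assessments (Protocol Table 2, SAP Table 1) also show an ECG at visit 1 only.

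**Protocol 7.1.1 (Definition of an Adverse Event).** An adverse event must develop or worsen during the study. Stable chronic conditions "that are present before study entry and do not worsen during this study will not be considered adverse events".

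**SAP 8.2 (Adverse Events).** For Part 1, "AEs occurring between ICF signing and end of Part 1 will be presented based on Enrolled analysis set". The tables concerned are Summary 15.3.1.2 (by system organ class and preferred term) and Summary 15.3.1.4 (by preferred term). For the safety analysis set, only events after the first drug administration are presented.

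**SAP Introduction.** Where protocol and SAP differ, the SAP prevails and the difference is explained in the clinical study report.

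**The concern.** The two documents classify the same finding, at the same visit, in opposite ways. This is no rare corner of the plan, because screening is the only scheduled ECG. A first tracing taken before any study treatment has no earlier study tracing to show that anything developed or worsened, so a finding on it is normally a baseline characteristic.

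The accuracy of the Part 1 safety tables is at stake. If the SAP rule is applied, a condition the participant brought into the study is counted as an event during it. It also appears as a screening abnormality in Summary 15.1.9.1 under SAP 5.6. If the site follows the protocol and the programmers follow the SAP, the classification may depend on who handled the record. In groups of 5 and 10, one such record visibly changes a percentage.

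**Working it through.** The plan states no figure on this point, so there is none to reproduce. The check traces one finding through the rules and then sizes it.

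**Tracing a clinically significant screening ECG finding in an enrolled participant**

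1. Does it fall inside the adverse event window? Protocol 3.14.1 says "A signed and dated informed consent form will be obtained before any screening procedures commence", and Protocol 7.1.2 starts adverse event recording at consent. The screening ECG is therefore inside the window.
2. How is it classified? As an adverse event under SAP 8.7, and as medical history under Protocol 7.6.
3. Which rule governs the analysis? The SAP, by its own precedence statement.
4. Where does it appear?

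| Output | Under SAP 8.7 | Under Protocol 7.6 |
|---|---|---|
| Part 1 adverse events, Summaries 15.3.1.2 and 15.3.1.4 | Counted | Not counted |
| Screening ECG, Summary 15.1.9.1 (SAP 5.6) | Shown | Shown |
| Part 2 treatment-emergent tables (SAP 8.2) | Not counted: before first dose | Not counted |
| Efficacy summaries | No effect | No effect |

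5. Does it meet the protocol's own definition? Not if the condition is stable and present before entry (Protocol 7.1.1). That section does allow an intermittently symptomatic pre-existing condition to be recorded when it occurs during the study, so the conflict with the definition is confined to stable findings.

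**Size**

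Inputs: planned numbers of 5 healthy controls, 10 asthma patients and 15 overall (SAP 5.1). Each participant is counted once per preferred term or system organ class (SAP 8.2). For a participant with no other adverse event, the increment in incidence is 1/n:

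- controls: 1/5 = 20 percentage points;
- asthma patients: 1/10 = 10 points;
- overall: 1/15 = 6.7 points.

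If the participant already has another adverse event, the proportion with any event does not move. Only the row for that term, and possibly its system organ class, changes.

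The asthma denominator can exceed 10. The enrolled set (SAP 3.1.4) holds everyone enrolled to Part 1, including patients who then fail inclusion criteria k or l, and Protocol 3.12 replaces patients who leave Part 2 after an exacerbation. As an assumed illustration, suppose 7 patients fail k or l, one below the 8 that triggers re-evaluation, and 10 others are randomized. Then n = 17 and the increment is 1/17 = 5.9 points.

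**The case against.** The strongest reply is that inflation of the tables may never happen. It needs an enrolled participant with a clinically significant screening ECG, and a site that enters it as an adverse event. Sites collect data under the protocol, which sends the finding to medical history, and a SAP precedence clause does not clearly change what sites record. Exclusion criterion f (clinically meaningful comorbidity) may remove some such people, and screen failures are outside the enrolled set. No drug is given in Part 1, comparing adverse events between controls and asthma patients is not a stated objective, and nothing is tested. All of this stands. It makes the effect conditional and small in consequence, but it does not reconcile two opposite rules.

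A reader might infer more than the documents support:

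- **That the control-versus-asthma comparison is biased by disease.** That argument rests on abnormal chest findings being commoner in asthma. Those come from physical examination, and the documents give no figure. Nothing in them suggests that ECG findings differ by group.
- **That physical examinations have the same defect.** SAP 8.5 says "Any physical examination finding that is judged by the investigator as clinically significant will be considered as an adverse event", but Protocol 7.7 has the same rule, so the documents agree. It can be read subject to the general definition in Protocol 7.1.1. Both documents also provide for listing newly occurring abnormalities. At most this is an ambiguity.
- **That the QTc threshold summary in SAP 8.7 is an error.** The SAP itself labels those thresholds as baseline, and moving the table would change no result.
- **That the whole SAP sentence is wrong.** Protocol 7.6 is silent on unscheduled ECGs, so that half of the sentence conflicts with nothing. A new finding there can properly be an adverse event.

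**Conclusion.** The contradiction is real, lies in current text of both documents, and is not explained by redaction or by the PDF conversion. Applied as written, the SAP rule puts a pre-treatment finding into the two Part 1 adverse event tables. Where the condition is stable, that is contrary to the protocol's adverse event definition.

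The increments of 20 points (controls) and about 10 points (asthma patients) rest on three assumptions: planned group sizes, a participant with no other adverse event, and handling under the SAP rule. The documents do not show that any such finding will occur, so the tables cannot be said to be inflated, only open to it. The reslizumab-versus-placebo safety tables and every efficacy result are untouched. Severity is minor: a classification rule that is wrong as written and easily corrected.

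**What to change.** In SAP 8.7:

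- remove the screening visit from the adverse event rule;
- state that clinically significant screening ECG findings are reported as medical history under Protocol 7.6, noting that SAP 5.6 already summarizes them;
- keep the adverse event rule only for unscheduled ECGs after screening, and only where the finding is new or worsened and so meets Protocol 7.1.1.

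The last item needs its own sentence in the SAP, because Protocol 7.6 does not cover unscheduled ECGs.

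The cost is a short SAP amendment, which SAP 2.5.2 allows for if approved before database lock. It needs no protocol change, no new data and no new output. If the SAP is left as it is, its introduction already commits the sponsor to explaining the difference in the clinical study report.
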